Change in pain intensity via the mobile app and as described by the subject using the Shortform McGill Pain Questionnaire-2 SF-MPQ-2 and the Patient Global Impression of Change (PGIC). The pain intensity scores will be measured twice daily using the mobile application and the SF-MPQ-2 will be completed during weeks 0,2,4,6 and 10 of the study. The PGIC will come completed at week 10.

These tools were chosen because a treatment should demonstrate a statistically and a clinically significant effect. Well-researched cutoff method suggests, that a 30% reduction of pain can be considered clinically significant (29). This level corresponds with a 2 points on a 0 to 10 pain intensity numerical rating scale (30). The Short-form McGill Pain Questionnaire (SF-MPQ-2) assesses the major symptoms of both neuropathic and nociceptive pain and can be used in studies of epidemiology, natural history, pathophysiologic mechanisms, and treatment response. Numerous studies have demonstrated its reliability, validity, and responsiveness in diverse samples of subjects with acute and chronic pain. Subjects rate their pain in sensory and affective terms and use a visual analog scale. The self-report measure Patient Global Impression of Change reflects a subject's belief about the efficacy of treatment. It is well studied and widely used in chronic pain clinical trials. PGIC is a 7-point scale depicting a subject's rating of overall improvement of a treatment intervention. Subjects rate their change as "very much improved," "much improved," "minimally improved," "no change," "minimally worse," "much worse," or "very much worse."

Changes in quality of life as measured by the Functional Assessment of Cancer The EORTC Quality of Life C-15- PAL measurement scale assessed at time of enrollment (week 0) week 6 and week 10 of the study. This is a validated questionnaire developed to assess the quality of life of palliative care cancer subjects.

Additional analysis includes changes in objective sleep measures using the mobile application and also The Sleep Scale developed for the Medical Outcomes Study. We will also look at the other characteristics of the pain that are automatically monitored with Quell/Sham device and its mobile application such as activity level.

5. Subject Selection

Study Population

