 Better and a definite improvement that has made a real and worthwhile difference (6)
 A great deal better and a considerable improvement that has made all the difference (7)

Patient's Signature:_

EORTC QLQ-C15-PAL (version 1)

We are interested in some things about you and your health. Please answer all of the questions yourself by circling the number that best applies to you. There are no "right" or "wrong" answers. The information that you provide will remain strictly confidential.

Ple Yo To	ease fill in your initials:	1			
		Not a All	t A Little	Quite a Bit	Very Much
1.	Do you have any trouble taking a short walk outside of the house?	1	2	3	4
2.	Do you need to stay in bed or a chair during the day?	1	2	3	4
3.	Do you need help with eating, dressing, washing yourself or using the toilet?	1	2	3	4
Dı	ring the past week:	Not a All	t A Little	Quite a Bit	Very Much
4.	Were you short of breath?	1	2	3	4
5.	Have you had pain?	1	2	3	4
6.	Have you had trouble sleeping?	1	2	3	4
7.	Have you felt weak?	1	2	3	4
8.	Have you lacked appetite?	1	2	3	4
9.	Have you felt nauseated?	1	2	3	4

Please go on to the next page

During the past week:	Not at All	A Little	Quite a Bit	Very Much
10. Have you been constipated?	1	2	3	4
11. Were you tired?	1	2	3	4
12. Did pain interfere with your daily activities?	1	2	3	4
13. Did you feel tense?	1	2	3	4
14. Did you feel depressed?	1	2	3	4

For the following question please circle the number between 1 and 7 that best applies to you

15. How would you rate your overall quality of life during the past week?

1 2 3 4 5 6 7

Very poor

Excellent

Date:	
Subject ID:	

Short-form McGill Pain Questionnaire 2 (SF-MPQ-2)

For this questionnaire, I will provide you a list of words that describe some of the different qualities of pain and related symptoms. Please rate the intensity of each of the pain and related symptoms you felt during the past week on 0 to 10 scale, with 0 being no pain and 10 being the worst pain you can imagine. Use 0 if the word does not describe your pain or related symptoms. Limit yourself to a description of the pain related to your surgery or pelvic pain.

1. Throbbing pain	none	0	1	2	3	4	5	6	7	8	9	10	worst possible
2. Shooting pain	none	0	1	2	3	4	5	6	7	8	9	10	worst possible
3. Stabbing pain	none	0	1	2	3	4	5	6	7	8	9	10	worst possible
4. Sharp pain	none	0	1	2	3	4	5	6	7	8	9	10	worst possible
5. Cramping pain	none	0	1	2	3	4	5	6	7	8	9	10	worst possible
6. Gnawing pain	none	0	1	2	3	4	5	6	7	8	9	10	worst possible

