2.5 Statistical Methods

Initially, a sample size of 20 participants per treatment group (active and sham) was selected to achieve 90% power to find a 20% difference in mean percent change in opioid consumption between the two groups with an estimated standard deviation of 22% and 80% power to detect the same difference with a standard deviation of 19% at a two-sided alpha = 0.05.

Bivariate associations between variables were assessed using statistical methods appropriate for the variable types (Fisher's exact for categorical variables; t-test, ANOVA or non-parametric equivalents for continuous variables). Baseline characteristics (demographics, other morbidities, baseline medication use, pain intensity and quality of life) were compared between the two treatment groups to assess effectiveness of randomization and identify important covariates for multivariable analyses. Associations between demographic variables and primary and secondary endpoints were examined. Sensitivity analyses comparing use of data from all participants with use of participants with complete data only was also performed. Agreement between different measures representing the same variable type (e.g., VAS and SF-MPQ-2) was assessed using correlation analyses.

Multivariable analysis with mixed effect regression models were used to assess the effect of treatment group on the primary and secondary outcomes over repeated measures controlling for potential confounders including opioid dose at baseline and using a group*time interaction term to determine differences in time course by treatment. Similar models were used to assess associations of treatment group with the secondary endpoints. Model fit assessed by Akaike's Information Criteria was used to determine the optimal covariance structure.

All statistical analyses were performed using SAS 9.2 (Cary, North Carolina).

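### The SAP assesses agreement between pain measures by correlation, which shows association only and cannot support a conclusion that the measures agree (minor)

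*SAP*

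**What the plan says.** SAP section 2.5 (Statistical Methods) gives both the aim and the method in one sentence: "Agreement between different measures representing the same variable type (e.g., VAS and SF-MPQ-2) was assessed using correlation analyses". It names no type of coefficient, no threshold, and no handling of repeated visits for this analysis. Protocol section 10 does not mention an agreement analysis.

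The measures involved are described in Protocol section 4 and the Appendix:

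- App score: "The pain intensity scores will be measured twice daily using the mobile application". The response scale of the app is not stated.
- SF-MPQ-2: section 4 says "Subjects rate their pain in sensory and affective terms and use a visual analog scale". The form in the Appendix instructs the subject as follows: "Please rate the intensity of each of the pain and related symptoms you felt during the past week on 0 to 10 scale". It has 22 descriptors, each scored 0 if it does not apply, followed by a 0-10 present-pain item. The instructions restrict answers to surgical or pelvic pain, and the present-pain item asks about pelvic pain.
- VAS: the SAP does not say which instrument this is. It could be the app score or a scale attached to the SF-MPQ-2.

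The secondary endpoints schedule the SF-MPQ-2 at weeks 0, 2, 4, 6 and 10. Under section 8.5, a week 8 visit held in the clinic mirrors Visit 3, which includes the SF-MPQ-2, so a subject can have six completions.

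**The concern.** Agreement asks whether two measures give the same value for the same subject. Correlation asks whether they rise and fall together. If Y = a + bX with b > 0, the correlation is 1 whatever a and b are, so neither a constant difference nor a difference in spread is visible.

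A systematic difference is plausible here. The descriptors use one-week recall, while app scores are entered twice a day. The form limits its answers to surgical or pelvic pain, and no such limit is stated for the app. An average over descriptors can also lie well below overall intensity. A high correlation reported under the label of agreement could lead a reader to treat the two pain measures as interchangeable in level, which the analysis would not have shown.

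**Working it through.** The plan gives no figure for this analysis, so there is nothing to reproduce. The check is whether a high correlation can sit beside poor agreement, and how far pooling visits would matter.

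**1. Correlation against concordance**

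Inputs, all assumed because the documents give none: correlation r = 0.95, equal standard deviation s on both scales, mean offset d = 2 points.

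- Concordance coefficient (Lin) = 2·r·s² / (2·s² + d²).
- Standard deviation of the differences = s·√(2(1 − r)) = s·√0.1.
- 95% limits of agreement = d ± 1.96 × that standard deviation.

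At s = 2: concordance = 2 × 0.95 × 4 / (8 + 4) = 7.6 / 12 = 0.63. The standard deviation of the differences is 2 × 0.316 = 0.632, and the limits are 2 ± 1.24, that is 0.76 to 3.24.

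| s (assumed) | r | Concordance | 95% limits of agreement |
|---|---|---|---|
| 1 | 0.95 | 0.32 | 1.38 to 2.62 |
| 1.5 | 0.95 | 0.50 | 1.07 to 2.93 |
| 2 | 0.95 | 0.63 | 0.76 to 3.24 |
| 2.5 | 0.95 | 0.72 | 0.45 to 3.55 |

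Every interval excludes 0, so these statistics show the offset that the correlation misses. Simulating 40 subjects on a bounded 0-10 scale (means 4 and 6, SD 2, 5,000 runs) gave a mean correlation of 0.945 and a mean concordance of 0.62.

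Two limiting cases:

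- If the offset were exactly 2 points for every subject, r would be 1.00 and the concordance at s = 2 would be 8 / 12 = 0.67.
- If Y = 0.5X with X spread evenly over 0 to 10, r is again 1.00 and the mean difference is 5 − 2.5 = 2.5 points.

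**2. Whether the SAP's own example is a fair target for agreement**

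Take a subject who rates four of the 22 descriptors 8 and the rest 0. The descriptor mean is 4 × 8 / 22 = 1.5, although the pain that is present is rated 8. Limits of agreement against an intensity score would report a large bias that comes from content, not from measurement disagreement. For this pair correlation is a reasonable tool, and the label is what is wrong.

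**3. Pooled visits, if they are pooled**

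Inputs: 40 subjects (the SAP says "a sample size of 20 participants per treatment group (active and sham) was selected", so 2 × 20), m = 5 visits, and an assumed intraclass correlation (ICC) of 0.6 on both measures, with the same correlation between the measures at both the between- and within-subject level.

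- Variance inflation for a correlation ≈ 1 + (m − 1) × ICC₁ × ICC₂ = 1 + 4 × 0.36 = 2.44.
- Standard error too small by √2.44 = 1.56, or about 1.6.
- Effective pairs = 200 / 2.44 = 82.

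Simulation under this set-up gave standard-error ratios of 1.54 to 1.57 and 81 to 84 effective pairs.

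Sensitivity: ICC 0.4 gives √1.64 = 1.28, and ICC 0.8 gives √3.56 = 1.89. At ICC 0.6, six visits give √(1 + 5 × 0.36) = √2.80 = 1.67.

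**The case against.** The strongest reply is that a VAS and the SF-MPQ-2 measure different things. Section 4 describes the SF-MPQ-2 in sensory and affective terms, so correlation is the natural convergent-validity analysis and only the word agreement is loose. That stands for this pair, and it is why the remedy there is to rename the analysis rather than replace it.

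Four stronger readings are tempting, and the documents do not support them:

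- **That the plan could overlook a difference it calls clinically significant.** Section 4 says "This level corresponds with a 2 points on a 0 to 10 pain intensity numerical rating scale", but the level meant is a 30% reduction in pain, a change within a subject. It is not a tolerance for an offset between instruments. The 2 points in the illustration are an assumed value.
- **That treatment conclusions are at risk.** A constant offset cancels in change over time and in the comparison of active with sham. More generally, the mixed models analyse each outcome on its own, and nothing in either document makes them depend on this analysis.
- **That an agreement analysis is ready to run on a common 0-10 scale.** The metrics of the app score and the VAS are not stated, the descriptor average differs in content from an intensity score, and the present-pain item as printed asks about pelvic pain, whereas the study enrols metastatic cancer of any type.
- **That repeated pairs were treated as independent.** The SAP does not say so. Separate correlations at each visit fit the text equally well.

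After these are set aside, the central point remains: the stated method cannot deliver the stated conclusion, and no other statistic in the documents fills the gap.

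**Conclusion.** The concern holds in a limited form. The sentence in SAP 2.5 claims to assess agreement with a method that measures association only. A correlation of 0.95 is compatible with a concordance coefficient of 0.32 to 0.72 for assumed standard deviations of 1 to 2.5 points and an assumed mean offset of 2 points. These figures show what correlation can hide. They do not predict the trial's data.

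The clustering point is conditional. If visits are pooled and the ICC is 0.6 on both measures, the naive standard error is too small by a factor of about 1.6 over five visits. If correlations are reported visit by visit, it does not arise.

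Severity is minor. This is a descriptive side analysis, and only what may be said about the interchangeability of the pain measures would change.

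**What to change.** 1. For the VAS or app score against the SF-MPQ-2 descriptor score, keep the correlation, report it as association or convergent validity, and draw no conclusion of agreement. State which instrument the VAS is.
2. Only where two items share the same 0-10 metric and the same pain target, add the mean difference with 95% limits of agreement and a concordance or intraclass coefficient. A candidate is the app intensity score against the SF-MPQ-2 present-pain item, once the app's metric is confirmed as 0-10 and the item's pelvic-pain wording has been reconciled with the study population. Pair scores that are close in time.
3. State whether correlations are computed per visit or across visits. If visits are pooled, use a method that allows for repeated measures on the same subject, both for the correlation and for any limits of agreement.

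The cost is one revised SAP sentence and at most one extra table from data already collected. Because the SAP is written in the past tense, the practical step may be to relabel or supplement the result in the report.

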8.7 Early Withdrawal Visit

- 1. Record any Adverse Experiences/troubleshoot any questions or concerns
- 2. Record changes to concomitant medications.
- 3. Review mobile application for adherence of use.
- 4. Perform and record vital signs.
- 5. Review Mobile Application Pain and Sleep assessment.
- 6. Review documentation of analgesic medication use.
- 7. Perform and record SF-MPQ-2 and Quality of life survey
- 8. Collect Quell/Sham device and delete mobile application from subject's phone
- 9. Administer the PGIC.
- 10. Provide subject with results of any preliminary data analysis pertinent to their involvement in the study.
- 11. Address any remaining question or concerns regarding subject's participation in the study.

9. Data Storage

All data will be transmitted and stored to HIPAA compliant encrypted standards.

Future research:

Subject information will be kept for at least 2 years after completion of this study and up to 20 years for future research that has not yet been planned. Future research using the data will first be approved by Scripps IRB. After 2031, the code that links the sample to the subject's traditionally-identifying information will be destroyed. Related de-identified health information will be kept indefinitely for future research studies at Scripps in secure databases.

10. Statistical Analysis

A biostatistician will perform all data analysis. The sample size (20 participants per group) achieves 80% power to find a 20% (absolute) difference in mean percent change in opioid consumption between the two groups with an estimated standard deviation of mean percent change of 22% and 90% power with an estimated standard deviation of 19% in both groups using a two-sided two-sample t-test with a significance level (alpha) of 0.05.

Descriptive statistics will be calculated for baseline characteristics of both study groups and to assess the effectiveness of the randomization. Repeated measures analysis will be used to assess changes in opioid medication use, pain assessments, and quality of life mesaures over time in the intervention group compared to the control group. Mid study analysis will be conducted with all data amassed around week 6 of all subjects enrolled.

11. Discontinuation and Replacement of Study Participants

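### The power statement is for a t-test on percent change, the SAP fits a mixed model with two candidate treatment terms, and no single contrast is named as the primary test

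*SAP*

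**What the plan says.** Protocol Section 10 gives 20 participants per group, a target of a "20% (absolute) difference in mean percent change in opioid consumption between the two groups", and power calculated "using a two-sided two-sample t-test with a significance level (alpha) of 0.05". It gives 80% power at SD 22% and 90% at SD 19%. For the analysis it says: "Repeated measures analysis will be used to assess changes in opioid medication use", along with pain and quality-of-life measures, comparing intervention with control over time.

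SAP 2.5 keeps the sample size but names no test for it. Its analysis statement is that "mixed effect regression models were used to assess the effect of treatment group on the primary and secondary outcomes over repeated measures". The model controls for potential confounders, including opioid dose at baseline, and is fitted "using a group*time interaction term to determine differences in time course by treatment".

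Protocol Section 4 lists the primary endpoint assessments as weeks 2, 4, 6, 8 and 10 and singles out no visit. Under Sections 3 and 8.2 the device is first fitted at week 2, after a two-week run-in, so the week 2 assessment describes untreated opioid use. Section 8.1 also records an opioid assessment at week 0.

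Neither document states which coefficient, contrast or visit is the primary test, whether the modelled outcome is dose or percent change, whether time is categorical or linear, or whether week 2 is a baseline or an outcome row.

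**The concern.** The t-test in the power statement compares one number per participant between arms. The mixed model offers two tests of treatment, and they ask different questions. The group effect asks whether the arms differ on average over the modelled visits. The group*time term asks whether the difference between arms changes from visit to visit.

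They can disagree on the same data. If every modelled visit is post-device, a device that lowers opioid use by week 4 and holds it there produces a group effect and no interaction. If the pre-device week 2 visit is modelled as an outcome, the interaction picks up the onset of benefit, but the group effect is averaged over a visit at which nobody was treated. If time enters as uncentred linear weeks, the group coefficient beside the interaction is the difference at week zero, before any device.

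So the conclusion on the primary endpoint can turn on a choice the plan leaves open, and the stated power is not the power of any term in the SAP model.

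**Working it through.** **Inputs from the documents.** n = 20 per arm; difference 20 points; SD 22 (or 19); two-sided alpha 0.05 (Protocol Section 10, SAP 2.5). Visits at weeks 2, 4, 6, 8 and 10; device from week 2 (Protocol Sections 3, 4 and 8.2).

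**Assumptions, not in the documents.** SD 22 applies at each visit; within-subject correlation ρ is 0.5 to 0.8, either compound symmetry (CS) or AR(1); no dropout; outcome on a percent-of-baseline scale; no precision gain from baseline adjustment.

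**Step 1. The plan's own figure.** Noncentrality = δ / (σ√(2/n)), 38 df, √(2/20) = 0.3162.
- SD 22: 20 / (22 × 0.3162) = 2.87, power 80.0%.
- SD 19: 20 / (19 × 0.3162) = 3.33, power 90.0%.

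The protocol's figures reproduce. SAP 2.5 attaches 90% to an "estimated standard deviation of 22% and 80% power to detect the same difference with a standard deviation of 19"%. Those pairs are swapped relative to the protocol and do not reproduce.

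**Step 2. Rows at weeks 4-10, benefit held at 20, 20, 20, 20.**

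Group effect (visit average): the SD of a participant's mean over T visits is σ√(1′R1)/T, where R is the correlation matrix; under CS this is σ√((1+(T−1)ρ)/T).

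| Covariance | SD of 4-visit mean | Noncentrality | Power |
|---|---|---|---|
| CS, ρ = 0.5 | 22√0.625 = 17.39 | 3.64 | 94% |
| CS, ρ = 0.8 | 22√0.85 = 20.28 | 3.12 | 86% |
| AR(1), ρ = 0.5 | 22√(8.25/16) = 15.80 | 4.00 | 97% |
| AR(1), ρ = 0.8 | 22√(12.384/16) = 19.35 | 3.27 | 89% |

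Group*time: λ = (n/2) m′(CΣC′)⁻¹m, where C takes differences between successive visits, Σ is the covariance matrix of the visits and m = Cδ. For a held effect m = 0, so λ = 0 and power equals alpha, 5%. This holds for any SD, correlation or time coding.

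**Step 3. Rows at weeks 2-10, effect 0, 20, 20, 20, 20.**

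Group effect: the average difference is (0 + 4 × 20)/5 = 16.

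| Covariance | SD of 5-visit mean | Noncentrality | Power |
|---|---|---|---|
| CS, ρ = 0.5 | 17.04 | 2.97 | 82% |
| CS, ρ = 0.8 | 20.16 | 2.51 | 69% |
| AR(1), ρ = 0.5 | 14.68 | 3.45 | 92% |
| AR(1), ρ = 0.8 | 18.72 | 2.70 | 75% |

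Group*time, linear time: contrast weights (−2, −1, 0, 1, 2) give 20 × (−1 + 0 + 1 + 2) = 40.
- AR(1), ρ = 0.5: SD 22√12 = 76.21, noncentrality 40 / (76.21 × 0.3162) = 1.66, power 37%.
- CS, ρ = 0.5: SD 22√5 = 49.19, noncentrality 2.57, power 71%.
- CS, ρ = 0.8: power 98%.

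Group*time, categorical time (4-df multivariate test): 62-95% under AR(1), and 79% to more than 99% under CS.

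**Step 4. Benefit that builds: 5, 10, 15, 20 at weeks 4-10.**
- Visit average: mean difference 12.5. Noncentrality runs from 12.5 / (20.28 × 0.3162) = 1.95 (48%) to 12.5 / (15.80 × 0.3162) = 2.50 (68%).
- Week 10 alone: 20 points at SD 22, 80%.
- Group*time, categorical: 22-38% under AR(1), 41-83% under CS.

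**Step 5. Type I error if either term counted.** For two independent tests, 1 − 0.95² = 9.75%. Simulation with 20,000 null trials per setting gave about 9-10%.

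**The case against.** The strongest reply is that SAP 2.5 does not make group*time its efficacy test. The models are said to assess the effect of treatment group; the interaction is given a separate, narrower purpose, the time course. A reader might infer that the trial has 5% power for a sustained benefit. The documents do not support that. The 5% requires the interaction to be the deciding test and week 2 to be left out of the outcome rows, and Protocol Section 4 lists week 2 as an assessment. On the same weeks 4-10 rows, the group effect meets or exceeds the 80% stated in the protocol.

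A reader might also infer that the trial's false-positive rate is doubled. No passage says that success on either term is enough, so the 9-10% is conditional.

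Nor is it an error in itself to size a trial with a t-test and analyse it with a mixed model. And the t-test is not tied to week 10: Protocol Section 10 names no visit, so the weeks 4-10 average is an equally legitimate primary contrast.

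All of this stands, and it limits the claim. It does not close the gap. The two readings of the outcome rows favour different terms, and the text does not say which term governs.

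**Conclusion.** The concern holds as a specification gap with consequences. The stated power describes a t-test on percent change, not the SAP model, and no deciding contrast is set. For one and the same held 20-point benefit, power runs from 5% to more than 99% across readings the text allows.

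Neither term is dependable under both readings. With weeks 4-10 as rows, group*time cannot see a held benefit. With week 2 kept, the group effect is diluted from about 86-97% to about 69-92%.

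The 5% result is algebra and needs no correlation assumption. The other figures rest on the assumed correlation of 0.5 to 0.8, a per-visit SD of 22 and no dropout. Baseline adjustment would raise the group-effect power by an amount that depends on how strongly baseline use predicts later use. Dropout would lower it.

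**What to change.** In SAP 2.5, state that:
- the sole primary test is one baseline-adjusted Quell-sham contrast from the same mixed model, over post-device data, at two-sided 0.05. It should be either the week 10 difference or the average over weeks 4-10, not both;
- pre-device data (week 0 and the run-in to week 2) enter only as baseline;
- the outcome scale and the coding of time are as specified, with categorical time the simplest choice for a visit contrast;
- group*time describes the time course and does not decide the primary endpoint;
- power is given for the chosen contrast, with the SD-power pairs brought back into line with the protocol.

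The choice has a trade-off. If the effect is held, week 10 has less power than the average (80% against about 86-97%). If it builds gradually, week 10 has more (80% against about 48-68%). Week 10 carries over the protocol's 80% at SD 22 directly; power for the average needs a stated correlation.

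The cost is a few sentences in the SAP and one contrast statement in SAS, with no new data. Because SAP 2.5 is written in the past tense, a contrast fixed after data were seen should be labelled as such and not presented as prespecified.

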The therapy pod is powered by a Lithium-Ion battery that provides 30-40 hours of therapy (4-7 days of typical use) if fully charged. The battery can be recharged in 2-3 hours by plugging the device into an AC adapter.

3. Study Design

The study is a single site, double blinded, placebo controlled randomized clinical trial. 40 subjects will be selected based on the inclusion criteria stated below and then randomized to either the intervention group or the placebo control group. Prior to the start of this study, a Controlled Substance Utilization Review and Evaluation (CURES) reports will be acquired to establish baseline number of opioid prescriptions for each subject. Subjects will track how consistently they are using pain medications, both opioids and non-opioids, during the two weeks prior to the start of the study. They will also provide twice daily recordings of their pain intensity via a mobile application. At the end of this two-week period, each subject will be fitted with a Quell or a sham device, including initial calibration to the subject's comfort level as described in the background section.

The sham device is identical to Quell in all aspects with one exception. While Quell delivers 1 hour of continuous stimulation during a therapy session, the sham device delivers three 2-minute periods of stimulation at 0, 28 and 58 minutes within the therapeutic session. This limited stimulation should have little to no analgesic effect but should suggest to the subject that they are receiving therapy.

Neither the principal investigator, nor the co-investigator or the subject will know if they are given a sham device or the actual Quell device. The study coordinators will be the only ones who will be aware of which intervention subjects receive. At the end of the study, subjects will be asked if they thought they had the sham or actual device. Both the principal and the co-investigator will be asked to identify which subjects they thought had Quell vs the sham device, prior to analysis of the data.

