8.1 Visit 1 (Week 0)

- 1. Review the study with the subject and obtain written informed consent and HIPAA authorization.
- 2. Assign the subject a unique screening number.
- 3. Record demographics data.
- 4. Record medical history, including a history of diagnosis date, and prior treatments.

- 5. Record concomitant medications.
- 6. Perform and record vital signs.
- 7. Download and set up mobile application on subject's phone.
- 8. Educate subject on how to use mobile application.
- 9. Have subject demonstrate knowledge of how to use application.
- 10. Perform and record the SF-MPQ-2, opioid assessment and Quality of life Assessment.
- 11. Provide them with their analgesic diary and educate them on how to use it
- 12. Schedule subject for visit 2 weeks.

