8.2 Visit 2 (Week 2)

- 1. Record any Adverse Experiences as needed.
- 2. Review Mobile Application Pain assessment.
- 3. Review documentation of analgesic use.
- 4. Perform and record vital signs.
- 5. Give subject Quell/Sham device, make sure subject properly calibrates.
- 6. Educate subject on how to use the device and to adjust intensity if needed and communicate that stimulation should feel "strong but comfortable".
- 7. Schedule follow up phone calls for subject to help trouble shoot and field questions on the device.
- 8. Perform and record the SF-MPQ-2.
- 9. Perform and record the results of the MOS Sleep Scale.
- 10. Schedule follow up visit for 2 weeks.

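### SAP 2.5 does not commit to adjusting each secondary endpoint for its own pre-device value, although the Protocol already schedules that value for four of these measures

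*SAP*

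**What the plan says.** SAP 2.5 describes mixed-effect models for the primary and secondary outcomes over repeated measures, "controlling for potential confounders including opioid dose at baseline", with a group*time term for differences in time course. It then adds: "Similar models were used to assess associations of treatment group with the secondary endpoints". No covariate other than baseline opioid dose is named.

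The same section compares baseline characteristics between arms, partly to find covariates for the multivariable models. Its list includes pain intensity and quality of life but not sleep. No threshold is given. The SAP does not say whether the pre-device visit is a response, a covariate or left out.

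The device is fitted at week 2, after a two-week run-in (Protocol section 3). Before or at that visit the Protocol schedules:

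- App pain, throughout the run-in: "They will also provide twice daily recordings of their pain intensity via a mobile application" (section 3).
- SF-MPQ-2 and quality of life at week 0: "Perform and record the SF-MPQ-2, opioid assessment and Quality of life Assessment" (section 8.1). SF-MPQ-2 is repeated at week 2 (sections 4 and 8.2).
- MOS Sleep at week 2: "Perform and record the results of the MOS Sleep Scale" (section 8.2).

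PGIC is taken at week 10, or at early withdrawal. Device-tracked sleep begins with device use. Neither has a pre-device value.

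**The concern.** The Protocol's hypothesis has two parts: less opioid use, and pain relief. The second part rests on the secondary models. For those endpoints the obvious prognostic covariate is the same measure before the device. Baseline opioid dose is a substitute, probably a weak one, for a pain, quality-of-life or sleep score.

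As written, the own baseline has two possible ways in. One is selection after a between-arm comparison. That uses the wrong criterion, because a prognostic baseline improves precision even when the arms are balanced on it, and it leaves the choice to be made after seeing data. The other is a group*time contrast with the pre-device visit among the responses, which behaves like a change score. With 20 subjects per arm, and no power figure for any secondary endpoint, the precision left unused could matter.

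**Working it through.** **Inputs.** Total sample: "40 subjects will be selected based on the inclusion criteria stated below" (Protocol section 3). Per arm: "The sample size (20 participants per group) achieves 80% power" (Protocol section 10). Test: "two-sided two-sample t-test with a significance level (alpha) of 0.05" (Protocol section 10). The documents do not give r, the correlation between the pre-device and follow-up values. It is assumed here to be 0.3 to 0.7. No dropout is assumed; no rate is given, and withdrawals after device use are not replaced (Protocol section 11.2).

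**The plan's own figure.** The only power statement is for the primary endpoint. For a 20-point difference with 20 per arm, the noncentral t with 38 degrees of freedom gives 80.0% at SD 22 and 90.0% at SD 19, which matches Protocol section 10. SAP 2.5 states the two pairs the other way round; that is a separate matter and does not affect this point. In SD units, the difference detectable with 80% power is 20/22 = 0.909 SD.

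**Variance of the group difference at one follow-up visit**, relative to a model that ignores the own baseline (= 1):

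- Change contrast: 2(1 − r).
- Own-baseline adjustment: 1 − r².
- Ratio of adjustment to change contrast: (1 + r)/2.

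| r | Change contrast | Own-baseline adjustment | Saving against ignoring baseline (r²) | Saving against change contrast ((1 − r)/2) |
|---|---|---|---|---|
| 0.3 | 1.40 | 0.91 | 9% | 35% |
| 0.5 | 1.00 | 0.75 | 25% | 25% |
| 0.7 | 0.60 | 0.51 | 49% | 15% |

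At r = 0.7, 0.51 is the share of variance that remains, so the saving is 49%. The two savings move in opposite directions as r rises.

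**Detectable difference at 80% power, for r = 0.3, 0.5, 0.7.** Ignoring baseline: 0.91 SD throughout. Change contrast, 0.909 × √(2(1 − r)): 1.08, 0.91, 0.70 SD. Own-baseline adjustment, with one degree of freedom spent: 0.87, 0.79, 0.65 SD.

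**Baseline opioid dose instead.** If its correlation with the endpoint is q (assumed 0.1 to 0.3), it removes q², or 1% to 9%.

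**The screening route.** At an assumed 0.05 level, a t-test with 20 per arm flags only differences above about 2.02 × √(2/20) = 0.64 SD. A chance imbalance of 0.5 SD would go unflagged. At r = 0.5 it shifts an unadjusted estimate by 0.5 × 0.5 = 0.25 SD.

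**Averaging over visits.** SF-MPQ-2 has three post-device visits in the section 4 schedule (weeks 4, 6 and 10). Under compound symmetry the variance of their mean is (1 + 2r)/3. Adjustment subtracts r²; a change contrast adds 1 − 2r.

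- r = 0.3: 0.533 unadjusted, 0.933 change, 0.443 adjusted.
- r = 0.5: 0.667, 0.667, 0.417.
- r = 0.7: 0.800, 0.400, 0.310.

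Adjustment therefore saves 17%, 38% and 61% against ignoring baseline, and 53%, 38% and 23% (rounded) against the change contrast. The single-visit figures are the more cautious ones.

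**What group*time tests with post-device responses only.** The week 10 minus week 4 contrast has variance (2/20) × 2(1 − r) = 0.2(1 − r), or 0.14, 0.10 and 0.06. A covariate that is constant over time cancels out of it, so these values are the same with or without the own baseline. The term also misses an effect that is present by the first post-device visit and then stable. For quality of life it would compare only week 6 with week 10.

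**The case against.** The covariate list in SAP 2.5 is open, baseline pain and quality of life are screened as candidates, and its wording on similar models can be read as putting each endpoint's own baseline in the place of opioid dose. The Protocol also speaks of changes in pain and quality of life (sections 4 and 10), and week 0 is in both questionnaire schedules. It is therefore plausible that the pre-device visit is in the model, as a response or through change scores.

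This stands against two stronger conclusions that a reader might draw. The first is that the trial discards its baselines. The text shows that the choice is unspecified and partly data-driven; it does not show exclusion. The second is that the plan loses up to 49% of variance. That figure applies only if the pre-device value is ignored. Against a change contrast the saving is 35% to 15%, and a change contrast already subtracts a chance baseline difference, leaving regression to the mean rather than the raw imbalance.

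It is also fair that unadjusted and change analyses are both valid under randomisation, so this is a matter of efficiency for endpoints the trial was not powered on. Protocol section 4 lists sleep as an additional analysis, so MOS Sleep may not be a secondary endpoint in the strict sense.

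What does not stand is that the open list settles the matter. Sleep is not in the screened list, screening is a poor rule for precision, and the change contrast is less precise than adjustment at every r below 1.

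**Conclusion.** The point holds as a free improvement. SAP 2.5 does not fix each secondary endpoint's own pre-device value as a covariate, and neither route it leaves open matches planned adjustment for precision. For r between 0.3 and 0.7, planned adjustment lowers the variance of the group difference at one visit by 35% to 15% if the model would otherwise test change, and by 9% to 49% if it would otherwise ignore the pre-device value. The documents do not show which applies.

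The figures rest on an assumed r, equal variances before and after the device, 20 per arm and no dropout; the averaged-visit and group*time figures also assume compound symmetry. The gain applies to the group difference at a visit or averaged over visits. It does not apply to a group*time term fitted to post-device visits alone. A reader might infer that the secondary estimates are biased or invalid; nothing in the documents supports that.

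**What to change.** In SAP 2.5, for each secondary or additional endpoint with a pre-device measure:

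- Name that measure as a fixed covariate whatever the between-arm comparison shows: the run-in mean of the app pain scores, week 2 SF-MPQ-2, week 0 QLQ-C15-PAL, and week 2 MOS Sleep. Baseline opioid dose may stay as a further covariate.
- Use only post-device visits as responses.
- Define the tested treatment effect as the adjusted group difference averaged over post-device visits, or at week 10; choose one. Keep group*time as a description of time course, not as the only test.

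A repeated-measures model that constrains the arms to a common baseline mean and tests the baseline-to-follow-up contrast is an equivalent alternative. State that PGIC and device-tracked sleep are analysed without a pre-device value.

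The cost is a few sentences, one degree of freedom per covariate-adjusted model and no new data. The SAP's past tense suggests that the analyses may already be done. If so, state how the pre-device value entered each model, and report the own-baseline-adjusted estimates alongside the others, labelled as added afterwards.
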